### **8.3 Lost to Follow up**

If a subject fails to return to the site for a required study visit the site must attempt to contact the subject and reschedule the missed visit as soon as possible and counsel the

Property of Haleon - Confidential

May not be used, divulged, published or otherwise disclosed without the consent of  
Haleon

Clinical Protocol Template, TMF-187821, v11.0. Parent SOP: **CCI**

subject on the importance of maintaining the assigned visit schedule and ascertain whether the subject wishes to and/or should continue in the study.

A subject will be considered lost to follow up if he or she repeatedly fails to return for scheduled visits and is unable to be contacted by the study site. Before a subject is deemed lost to follow up, the investigator must make every effort to regain contact with the subject (where possible, 3 telephone calls and, if necessary, a certified letter to the subject's last known mailing address or local equivalent methods). These contact attempts should be documented. If contact is made with the subject, the investigator should inquire about the reason for withdrawal, request that the subject return all products that they had been dispensed and if appropriate request that the subject return for a final visit and follow-up with the subject regarding any unresolved AEs.

Final safety assessments may be carried out when the subject returns to the study site, at the investigator's discretion, which could include the following:

Should the subject continue to be unreachable, he/she will be considered to have withdrawn from the study and lost to follow up.

Lack of completion of all or any of the early termination procedures will not be viewed as protocol deviations so long as the subject's safety was preserved.

If the subject withdraws from the study and withdraws consent for disclosure of future information, no further evaluations should be performed, and no additional data should be collected. The sponsor may retain and continue to use any data collected before such withdrawal of consent.

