## **9 STUDY PROCEDURES**

This section lists the procedures to be completed at each planned study visit. The timing of each procedure is listed in the [Schedule of Activities](#) section.

Adherence to the study design requirements, including all procedures are essential and required for study conduct.

This section lists the procedures to be completed for each planned study time point. However, as per nature of RWE studies, if a subject fails to complete their daily questionnaires at any timepoint post-baseline, subjects will be permitted to continue in the study with missed dates recorded in the e-dairy.

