### **9.2.2 Days 1-21**

The number of days each subject will actively engage with the study will vary according to the baseline measurements. Voltaren Gel use will be limited to 21 days, but study

Property of Haleon - Confidential

May not be used, divulged, published or otherwise disclosed without the consent of  
 Haleon

Clinical Protocol Template, TMF-187821, v11.0. Parent SOP: [CCI](#)

subjects are allowed to stop using the product if they do not feel the need to continue using it (e.g., if the pain subsides). Study subjects will be told to use the products as per label instructions. Actigraph will collect mobility and sleep-related information continuously (24/7) throughout the study.

All questionnaires will be provided at pre-specified time-points during the study ([please see schedule of activities table](#)). Safety, adverse events, and use of concomitant medications will be monitored throughout the study. If a subject stops using the product before Day 21 (post baseline), they will be prompted to complete all relevant questionnaires before concluding the study.

The following assessments will be completed by subjects during the study period:

- Subjects will report any changes in health, concomitant medications, or non-drug treatments/procedures.
- Subjects will use Actigraph and complete additional QoL questions each day.
- Subjects will complete an eDiary to record product use each day.
- Subjects will report any adverse events.
- Subjects will report the end of product use and answer end of the study questions prior to exiting the study.

Subjects who do not use the product at all throughout the study will be considered as dropouts. Partial usage of the product across the treatment period (Day 7 to Day 21) is allowed to capture RWE usage of the product.

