#### **7.4.7.3 Exploratory Variables**

##### **Elapsed time from Voltaren Gel use to achieving time to meaningful pain relief to end of study**

Date of meaningful pain relief is defined as the earliest date where:

- The answer to "Did you use yesterday the Voltaren Gel as per label and leaflet instructions?" is "No"  
AND
- The answer to "If No, please specify the reason:" is "No pain anymore"

On the 'Study Product Use' eDiary page.

The time to event is derived in days as:

- Date of event/censoring – date of First Treatment Administration +1

Date of First Treatment Administration is derived as explained in section 7.1.

For patients who complete or discontinue the study without event occurrence, the patients are considered "censored" and the date of censoring is the date of study discontinuation recorded on the 'Study Termination' eCRF page.

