## Elapsed time from Voltaren Gel use to achieving time to meaningful pain relief to end of study

Time to meaningful pain relief is estimated using Kaplan-Meier method. This includes, patients with event, patients censored, time to meaningful pain relief (days), median with 95% confidence interval, Q1 and Q3. Time to event and censoring are derived as explained in section 7.4.7.3.

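### Time to meaningful pain relief: the event needs a completed eDiary page, but event-free subjects are censored at study termination, so days after the last diary count as observed without relief

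*SAP*

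**What the plan says.** **Event.** SAP 7.4.7.3: "Date of meaningful pain relief is defined as the earliest date where" the subject answers on the 'Study Product Use' eDiary page that the gel was not used and gives absence of pain as the reason. No other source can supply an event.

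**Censoring.** The same section treats every subject without such an entry as censored. For these, "the date of censoring is the date of study discontinuation recorded on the" termination page of the eCRF. This covers completers as well as early withdrawals.

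**Analysis.** SAP 8.2.4: "Time to meaningful pain relief is estimated using Kaplan-Meier method", with the median and its 95% CI, Q1 and Q3. It adds no rule of its own: "Time to event and censoring are derived as explained in section 7.4.7.3". SAP 8.2.5.1 replaces no missing data except adverse event dates. Protocol 13.3.4 gives no censoring rule.

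**Diary conduct.** Protocol 9.2.2: "Subjects will complete an eDiary to record product use each day". Protocol 9 accepts gaps: "if a subject fails to complete their daily questionnaires at any timepoint post-baseline, subjects will be permitted to continue in the study". Protocol 8.3 has a subject declared lost only after repeated missed visits and contact attempts ("where possible, 3 telephone calls and, if necessary, a certified letter").

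**The concern.** Follow-up for the event ends with the last diary page, while time at risk ends with a date on a different form. Nothing in either document links the two. A subject who stops filling in the diary but stays in the study, or who is pursued for some time before being declared lost, remains in the denominator on days when an event cannot be seen.

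The tabulated quartiles, the median with its interval, and the plotted curve would then reflect diary drop-off as well as pain relief. This is the only estimate that serves the exploratory objective on time to meaningful relief. In a single-arm study there is no comparator in which the same distortion could cancel.

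**Working it through.** **1. Plan's own figure.** There is none. The documents state no event count, relief rate or precision for this endpoint.

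**2. Direction.** On day k let d_k be the recorded events and n_k the number at risk. Kaplan-Meier relief is 1 − Π(1 − d_k/n_k). Moving the censoring date from last diary to termination leaves every d_k unchanged and can only raise n_k. Each d_k/n_k is therefore equal or lower, cumulative relief is equal or lower, and Q1, median and Q3 are equal or later. This needs no assumption about how many subjects stop the diary or why.

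**3. Inputs for the size (all assumed).**
- Constant daily relief hazard h, with true Day 21 relief F. For F = 50%, h = 1 − 0.5^(1/21) = 0.03247.
- A fraction f of subjects goes silent, with last diary day u uniform on days 1 to 20 and unrelated to relief.
- Termination 1 day after the last diary, 7 days after it (both no later than Day 21), or at Day 21.

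**4. Formula.** Let O_k be the proportion event-free and still completing the diary on day k, and U_k the proportion silent, without a recorded event and not yet terminated. Under the SAP rule the estimated hazard is h × O_k/(O_k + U_k). Under last-diary censoring it is h.

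*Example: day 11, f = 25%, 7-day gap.* O = 0.5^(10/21) × (0.75 + 0.25 × 10/20) = 0.7189 × 0.875 = 0.629. U = (0.25/20) × Σ 0.5^(u/21) over u = 4 to 10 = 0.0125 × 5.568 = 0.070. The hazard is 0.03247 × 0.629/0.699 = 0.0292 instead of 0.0325.

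*Check where all stay to Day 21.* Nobody is censored earlier, so the estimate is the recorded proportion: (1 − f)F + f × mean over u of [1 − (1 − h)^u]. For F = 50% that mean is 0.280, giving 0.500 − 0.220f, which is 47.8%, 44.5% and 41.2% for f = 10%, 25% and 40%.

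**5. Results: estimated Day 21 relief, true value 50%.**

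| Gap from last diary to termination | f = 10% | f = 25% | f = 40% |
|---|---|---|---|
| 1 day | 49.8% | 49.5% | 49.2% |
| 7 days | 48.9% | 47.0% | 44.9% |
| All stay to Day 21 | 47.8% | 44.5% | 41.2% |

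Last-diary censoring returns 50% in every cell. A simulation with 400,000 subjects per setting agrees to about 0.1 point. With no diary gaps the two rules coincide.

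**6. Other relief rates, all staying to Day 21.** True relief 30%: 28.6%, 26.5%, 24.4%. True relief 70%: 67.2%, 63.0%, 58.9%; here the median moves from day 13 to day 14 (f = 25%) or day 15 (f = 40%).

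**The case against.** The strongest reply is about size and cure, since the text of the rule is not in doubt.

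- **The gap may be short.** The investigator reviews the diary on Days 7, 14 and 21 (Protocol 9.3), compliance is monitored through it (13.3.6.1), and subjects who stop the gel are prompted to complete their questionnaires (7.7, 9.2.2). Protocol 9.2.3 ends the study the day after last treatment for early stoppers, although 8.1 asks those discontinued from the product to stay for the remaining assessments. This makes widespread silence up to Day 21 less plausible but does not exclude gaps.
- **The 25% is not a diary rate.** A reader might take the plan's dropout allowance as the silent fraction and conclude that relief is understated by about a tenth. The documents do not support that: the allowance is for leaving the study, and a promptly recorded withdrawal leaves little gap.
- **The median.** A reader might also infer that the median becomes unreachable. That follows only from setting true relief at exactly 50%. Even with complete diaries, 195 subjects would reach the median in half of such trials, because 98 or more events and 97 or fewer are equally likely.
- **Last-diary censoring can err too.** If only subjects who never get relief go silent, the termination rule returns the true 50%, while last-diary censoring gives about 53% (f = 10%) or 59% (f = 25%). The documents do not say which mechanism applies.
- **Other losses remain.** If relief is reported on one day only and 20% of diary days are missed at random, 50% becomes 40.0% under the SAP rule and 40.4% under last-diary censoring. If 25% of relief reports are lost because the subject leaves without a further diary entry, the figures are 40.4% and 40.6%.

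All of this stands as a limit on size and on what the fix can achieve. None of it supplies a reason to count days without a diary as observed.

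**Conclusion.** The point holds. The censoring rule in SAP 7.4.7.3 treats days after the last diary as relief-free follow-up, and no other section repairs it. The direction relative to last-diary censoring is certain. Calling it bias against the truth requires that diary stopping be unrelated to relief.

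The size cannot be fixed from the documents. At true Day 21 relief of 50% and 10% to 40% silent, it runs from under 1 point (1-day gap) through about 1 to 5 points (7 days) to about 2 to 9 points (all stay to Day 21), and is nil if diaries run to termination. The last case is the upper end of the assumed range, not an expectation.

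The endpoint is exploratory and descriptive, with no test attached. No primary, secondary or safety result is affected.

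**What to change.** In SAP 7.4.7.3:

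1. Censor event-free subjects, completers included, at the date of their last completed 'Study Product Use' eDiary entry. Events are already dated by the diary entry, so both dates would then come from one source. Apply any end-of-follow-up cap equally to events and to censoring.
2. Report how many subjects have more than 1 day between last diary and termination.
3. Keep the termination-date rule as a sensitivity analysis.
4. Add a sensitivity analysis that counts the discontinuation reason 'Withdrawal due to no pain' (SAP 7.4.1) as an event. The present definition does not use it.

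**Cost.** A short SAP edit, one changed derivation and two supplementary runs, all on data already collected. Follow-up becomes slightly shorter and the interval wider. Relief may be overstated if subjects without relief are the ones who stop the diary; item 3 would show how far that matters. Scattered missed diary days are not recovered by any of these steps and should be stated as a limitation.

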## 7.4.8 Safety Variables

### Adverse Events

An adverse event (AE) is defined as “any untoward medical occurrence in a clinical study subject, temporally associated with the use of a study product including any washout or lead-in product (or medical device), whether or not considered related to the study product, including any washout or lead-in product (or medical device)”.

An AE can therefore be any unfavourable and unintended sign (including an abnormal laboratory finding), symptom, or disease (new or exacerbated) temporally associated with the use of a study product including any washout or lead-in product (or medical device).

AE data are collected from the time that informed consent was given for the duration of the trial on the ‘Adverse Events’ eCRF page.

The following information is recorded:

- AE term;
- Start date/time;
- End date/time (or ongoing);
- Severity (“Mild”, “Moderate”, or “Severe”);
- Serious (“Yes”, “No”)
  - if AE is serious:
    - Death (‘No’, ‘Yes’) if yes then also date of death;
    - Life threatening (‘No’, ‘Yes’);
    - Hospitalization (‘No’, ‘Yes’) if yes then also start and end date;
    - Significant Disability (‘No’, ‘Yes’);
    - Congenital Anomaly or Birth Defect (‘No’, ‘Yes’);
    - Other Medically important event (‘No’, ‘Yes’);
- Outcome (“Fatal”, “Not recovered/ not resolved”, “Recovered/ resolved”, “Recovered with sequelae / resolved with sequelae”, “Recovering / resolving”, or “Unknown”);
- Relationship to study drug (“Unknown”, “Not Related”, “Unlikely”, “Possible”, “Probable”, or “Definite”);
- Action taken with study treatment (“Dose not changed”, “Dose increased”, “Dose rate reduced”, “Dose reduced”, “Drug interrupted”, “Drug withdrawn”, “Not applicable”, or “Unknown”);
- Other action taken:
  - None (‘No’, ‘Yes’);
  - Medication prescribed (‘No’, ‘Yes’);
  - Device removed (‘No’, ‘Yes’);
  - Surgery (‘No’, ‘Yes’);
  - Other (‘No’, ‘Yes’);

### Pre-Treatment Adverse Events

Pre-treatment AEs are defined as AEs that started during the pre-treatment period (date of informed consent up to the date/time of first study treatment administration).

## **Serious AE**

A Serious AE is any AE where the 'Serious' flag has been marked as 'Yes'.

Serious AEs have the following additional information recorded: did AE result in death, was AE life threatening, did AE result in initial or prolonged hospitalization, did AE result in disability or permanent damage, was AE associated with a congenital anomaly or birth defect, and was AE a medically important event not covered by other serious criteria.

## **Treatment-Emergent Adverse Events (TEAEs)**

A treatment-emergent adverse event (TEAE) is defined as an AE that started on or after the date of the first study treatment administration and is derived using start/onset and stop dates only.

Missing AE dates are handled according to the same rules as specified for concomitant medications in Section 7.2.

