## **9.2 Study Period**

### **9.2.1 Baseline Period**

The number of days each subject will actively engage with the study will be up to 28 days including baseline ([See Appendix](#)).

Study subjects who fulfil criteria and deemed suitable by the investigator for participation will be provided with the Actigraph wearable device which will measure aspects of functional mobility during the baseline period. The baseline period will last between 3 (minimum) and 7 days (maximum), to collect enough information on both subjective and objective aspects of mobility and sleep quality. End of baseline period will be considered day 0.

The baseline period will be variable and will depend on study subjects reaching  $\geq 40$  mm  $\leq 70$  mm of self-reported pain on the pain intensity visual analogue scale (VAS). Once the subject reaches any value at this level on the VAS scale, even for a single observation, the baseline period will be terminated, and study phase can commence.

At the end of the baseline period, the site staff will dispense the study product to the subject to take home and use throughout the study period as per label instructions. Before they start using the product, study subjects will complete the questionnaires to collect information on their baseline levels of quality of life and subjective perceptions of mobility and exercise capacity.

All medications taken during the 60 days prior to the screening visit and throughout the trial (other than study medication) will be recorded on the eCRF.

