**Events Meeting the AE Definition:**

- Any abnormal laboratory test results (haematology, clinical chemistry, or urinalysis) or other safety assessments (e.g. ECG, radiological scans, vital sign measurements), including those that worsen from baseline, considered clinically significant in the medical and scientific judgment of the investigator (i.e., not related to progression of underlying disease).
- Exacerbation of a chronic or intermittent pre-existing condition including either an increase in frequency and/or intensity of the condition.
- New conditions detected or diagnosed after informed consent signing (prior to study product administration) even though it may have been present before the start of the study.
- Signs, symptoms, or the clinical sequelae of a suspected drug-drug interaction.
- Signs, symptoms, or the clinical sequelae of a suspected overdose of either study product or a concomitant medication. Overdose per se will not be reported as an AE/SAE unless it is an intentional overdose taken with possible suicidal/self-harming intent. Such overdoses should be reported regardless of sequelae.
- The signs, symptoms, and/or clinical sequelae resulting from lack of efficacy will be reported as AE if they fulfill the definition of an AE. Also, "lack of efficacy" or "failure of expected pharmacological action" constitutes an AE.

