## 11.5 Follow-up of AEs and SAEs

The investigator is obligated to perform or arrange for the conduct of supplemental measurements and/or evaluations as may be indicated or as requested by Haleon to elucidate as fully as possible the nature and/or causality of the SAE or AE. This may include additional laboratory tests or investigations, histopathological examinations, or consultation with other health care professionals.

New or updated information will be recorded on the AE eCRF page and on the SAE form (subject to the classification of the AE).

The investigator will submit any updated SAE data to Haleon within 24 hours of receipt of the information.

The investigator will submit any updated SAE data to Haleon within 24 hours.

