## **TEAE Leading to Permanent Withdrawal of Study Treatment**

A TEAE leading to permanent withdrawal of the Study Treatment is defined as a TEAE where the action taken with study treatment is recorded as "Drug withdrawn".

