## 10.7 Safety Results

### 10.7.1 Adverse Events

#### 10.7.1.1 Brief Summary of Adverse Events

An Overview of AEs including but not limited to

- the number of subjects with at least one AE;
- the number of subjects with at least one pre-treatment AE;
- the number of subjects with at least one TEAE;
- the number of subjects with at least one Serious TEAE;
- the number of subjects who permanently discontinued Study Treatment due to a TEAE;
- the number of subjects with a TEAE related to study treatment;
- the number of subjects who had a TEAE with outcome of death
- the worst severity of any TEAE experienced by each subject with at least one TEAE

is summarized by treatment and overall, for the SAF in Table CCI [REDACTED]

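### AEs that begin in the baseline period and turn serious or fatal, or stop the gel, after first use fall outside every treatment-period safety count the SAP specifies

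*SAP*

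**What the plan says.** SAP 7.4.8 states the collection window: "AE data are collected from the time that informed consent was given for the duration of the trial". Protocol 9.2.1 puts 3 to 7 days of baseline between screening and the first gel, so AE records with onset before any gel are expected.

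The SAP then divides AEs by onset. On one side, "Pre-treatment AEs are defined as AEs that started during the pre-treatment period". On the other, a TEAE is "an AE that started on or after the date of the first study treatment administration and is derived using start/onset and stop dates only". Neither definition mentions a change in severity or seriousness after first use.

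The derived categories inherit the split. A serious TEAE is a TEAE with the serious flag set. A TEAE leading to death is a TEAE with a fatal outcome. A TEAE leading to permanent withdrawal "is defined as a TEAE where the action taken with study treatment is recorded as" *Drug withdrawn*.

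The overview in SAP 10.7.1.1 has one row for any AE and one for pre-treatment AEs. All its other listed rows are TEAE rows, including "the number of subjects who permanently discontinued Study Treatment due to a TEAE". The tables by system organ class and preferred term in SAP 10.7.1.2 cover TEAEs, serious TEAEs and related TEAEs.

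The safety endpoint in Protocol Table 3-1 is the number and percentage of subjects with AEs or SAEs during treatment.

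**The concern.** The endpoint concerns what happens on treatment, but the SAP sorts records only by when they began. An AE that starts a few days before the gel and becomes serious in the second week of use is a serious event on treatment in any ordinary sense, yet the SAP classes it as pre-treatment for good. The withdrawal row shows this most plainly: the gel can be withdrawn only from someone who has started it, so a withdrawal is a treatment-period event whatever the onset date of the AE behind it.

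At stake are the rows a reader looks at first: serious events, deaths, and stopping the product because of an AE. These counts are expected to be low, so one omitted record can change a row from zero to one.

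**Working it through.** The documents state no figure on this point, so there is nothing to reproduce. The check is to apply the SAP's definitions to example records and then see what can be said about size.

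**Step 1. Apply the rules.** Inputs: the definitions in SAP 7.4.8 and the rows in SAP 10.7.1.1. Records A to D have a known onset 3 days before first use. Record E has its onset on day 4 after first use.

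| Record | Any AE | Pre-treatment AE | TEAE | Serious TEAE | Withdrawal TEAE | Fatal TEAE |
|---|---|---|---|---|---|---|
| A. Mild, becomes severe, same record updated | 1 | 1 | 0 | 0 | 0 | 0 |
| B. Becomes serious | 1 | 1 | 0 | 0 | 0 | 0 |
| C. Becomes fatal | 1 | 1 | 0 | 0 | 0 | 0 |
| D. Gel withdrawn | 1 | 1 | 0 | 0 | 0 | 0 |
| E. As A, but worsening entered as a new AE | 1 | 0 | 1 | 0 | 0 | 0 |

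B, C and D follow from the definitions. A and E are the same clinical course and differ only in how the site recorded it.

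**Step 2. Do the documents settle A against E?** Protocol 11.1 lists as an AE "Exacerbation of a chronic or intermittent pre-existing condition including either an increase in frequency and/or intensity of the condition", which points towards a new record, but it speaks of pre-existing conditions and gives no instruction for an AE already on file. Protocol 11.5 says "New or updated information will be recorded on the AE eCRF page and on the SAE form", which points towards updating, but the AE page is the form used for every AE, new or old. Neither tells the site which to do.

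**Step 3. Where does the record still appear?** A to D remain in the any-AE and pre-treatment rows (SAP 10.7.1.1) and in the AE listing (SAP 10.7.1.3). If the subject leaves the study, an AE or death can be the primary reason in the disposition table (SAP 7.4.1 and 10.1). Protocol 8.1, however, has a subject who stops the gel early stay in the study for the remaining assessments unless withdrawal is needed. Such a subject has no study-discontinuation reason, so record D is in no disposition row either.

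**Step 4. Size.** Two calculations are possible, and neither estimates the number affected.

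- Share of AE records starting before the gel, assuming a constant onset rate over baseline plus 21 treatment days: 3/(3+21) = 12.5% with the shortest baseline and 7/(7+21) = 25% with the longest.
- Expected number of subjects omitted = 195 × p × q. Here 195 is planned enrolment, p is the share of subjects with a baseline-onset AE, and q is the share of those whose AE escalates on the same record. Both p and q are assumptions, because the documents give neither.
  - p = 1%, q = 5%: 195 × 0.01 × 0.05 = 0.1
  - p = 5%, q = 10%: 195 × 0.05 × 0.10 = 1.0
  - p = 10%, q = 25%: 195 × 0.10 × 0.25 = 4.9

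**The case against.** Onset-based classification is a stated and transparent convention. The study is single-arm with descriptive safety, so no between-group comparison is biased. The overview's contents are introduced as a non-exhaustive list, the table shells are in a separate document, and Protocol 13.3.3 commits to tabulating AEs and SAEs without a TEAE restriction. A row for all SAEs may therefore exist in the shells. This stands as a limit: the point concerns what the SAP specifies, and the SAP specifies no such row.

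Four stronger readings are tempting, and the documents do not support them.

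- *A reader might infer that these events vanish from the report.* They do not. Step 3 shows where they remain, although none of those places is a treatment-period safety count.
- *A reader might infer that any worsening of a baseline AE is missed.* That depends on how the site records it, which is unsettled (Step 2).
- *A reader might infer that the TEAE rule can only undercount.* SAP 7.2.2 can impute a missing start to first use, which adds TEAEs. The TEAE window also has no end date, so AEs starting after the last application count although the endpoint is limited to treatment. The downward direction holds only for records with a known baseline onset.
- *A reader might infer that 12.5% to 25% of AEs are misclassified.* That is the assumed share starting before the gel. A baseline AE that does not escalate is correctly pre-treatment.

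The objection on cost is partly right. SAP 7.4.8 lists one severity and one serious flag per AE, with dates only for death and hospitalisation. A worsening clause therefore needs dates that are not collected. The withdrawal and death counts do not.

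**Conclusion.** The point holds for AE records with a known baseline onset that become serious or fatal, or carry *Drug withdrawn*, after first use: they enter no treatment-period safety count that the SAP specifies. That follows from the definitions and needs no assumption. Gel withdrawal is the firmest case, since it presupposes that the gel was started and may not show in disposition. For worsening without seriousness, the gap is conditional on the site updating the existing record.

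The number of subjects is unknown. The range of about 0.1 to 4.9 in Step 4 rests wholly on assumed inputs, and a short baseline makes a small number likely. The change is still worth making, because the records concerned are the most consequential ones and the endpoint is defined by the treatment period.

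**What to change.** In SAP 7.4.8 and 10.7.1.1:

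(a) Count AEs with action *Drug withdrawn*, and AEs that are serious or fatal after first use, in the safety population regardless of onset. The action, seriousness, death-date and hospitalisation-date fields are already collected. Seriousness on another criterion carries no date, so for a baseline-onset record it joins the query in (b).

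(b) Extend the TEAE definition to AEs with earlier onset that increase in severity or become serious on or after first use. Send a query for the date of change on the few baseline-onset AEs still ongoing at first use.

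The cost is revised SAP wording, a changed flag in the AE dataset, a few queries before database lock, and slightly less favourable counts. SAP version 2.0 already follows the data review meeting. If the queries can no longer be sent, the withdrawal, death and hospitalisation parts of (a) can still be done from existing data.
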